COVID-IVIG Protocol Cover Page

Study Title: Randomized Open Label Study of Standard of Care Plus Intravenous Immunoglobulin(IVIG) Compared to Standard of Care Alone in the Treatment of COVID-19 Infection

NCT Number: NCT04411667

Document Date: 19May2020

Protocol name: COVID-IVIG

Principal Investigator: [name]; [contact]; [contact]
IRB # 2004902

Title: Randomized Open Label Study of Standard of Care Plus Intravenous Immunoglobulin (IVIG) Compared to Standard of Care Alone in the Treatment of COVID-19 Infection

Primary Objective:

1. To identify whether or not IVIG can halt the progression to respiratory failure requiring mechanical ventilation in subjects admitted to the hospital with confirmed COVID-19.

Secondary Objectives:

1. To identify whether adding IVIG to the standard of care will reduce days requiring oxygen therapy.
2. To identify whether adding IVIG to the standard of care will reduce total hospital days.

Hypothesis: We hypothesize that the addition of IVIG will be beneficial in abating acute lung injury in subjects with SARSCoV-2 induced hypoxia that results in organ injury in such patients.

Background: Coronaviruses has been known zoonotic pathogens since the early 1970's. Bats have been identified as the main natural reservoir and domesticated animal intermediary species (e.g., camels, cats) have facilitated transmission to humans. In late 2019, a novel coronavirus (SARS-CoV-2) emerged in humans, originating in Wuhan, China and spreading across the globe as a pandemic, causing coronavirus disease of 2019 (COVID-19).

The current mortality rate (17MAR2020) is not well described because of the shortage of laboratory testing assays worldwide. Using WHO data on the cumulative number of deaths to March 1, 2020, mortality rates would be 5.6% (95% CI 5.4–5.8) for China and 15.2% (12.5–17.9) outside of China⁸.

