1. Confirmed COVID-19 positive test result (including presumptive positive).
2. Hospitalization
3. Requiring ≥ 4 liters/min O_2 nasal cannula to maintain oxygen saturation $\geq 92\%$, but not mechanically ventilated
4. Age ≥ 18 years old.
5. Access to a phone in the hospital room or an electronic device that is capable of receiving phone calls and/or video calls and/or e-mail.
6. Able to read/write/speak English or Spanish fluently.
7. Subjects must have the capacity to provide consent or an appropriate Legally Authorized Representative (LAR) to provide informed consent.
8. Negative pregnancy test for women of childbearing potential.

Exclusion Criteria:

1. Severe allergy to any IVIG product formulation
2. History of DVT, PE, thromboembolic stroke or other thrombotic events

3. Hypersensitivity to corn. Octagam® contains maltose which is a sugar derived from corn.
4. Uncontrolled hypertension (SBP>180 mm Hg or DBP>120mmHg)
5. Active participant in another research treatment study
6. Mechanically ventilated patient
7. Code status is Do Not Resuscitate or Do Not Intubate

Age of Subjects: ≥18 years of age

Gender of Subjects: Either male or female

Racial and Ethnic Origin: Non-specific

Vulnerable Subjects: Hospitalized subjects

Study Design: Investigator initiated, open label, multicenter, two arm, randomized study to compare the impact of adding IVIG to the Standard of Care (SOC) to the SOC without IVIG. Randomization ratio will be 1:1.

Procedures and Study Visits:

1. The PI will be notified of a COVID-19 tested positive patient via hospital generated alert.
2. The PI or designee will prescreen the patient using the inclusion and exclusion criteria.
3. PI or Sub-I will contact the study team, if the patient passes prescreening.
4. The CRC will obtain an informed consent from the subject or LAR either electronically utilizing DocuSign® or with a paper copy utilizing an impartial witness:
 - a. The research team will utilize DocuSign® for the signing of the consents in order to be compliant with the infection control measures taken place for Highly Infectious Diseases. Below are the steps of the DocuSign® procedure:

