5. A urine or blood pregnancy test will be ordered using urine or blood previously collected for routine care for subjects of childbearing potential who have passed all the other screening criteria and signed consent. If no leftover urine or blood is available, the patient will be asked to take a urine pregnancy test. If the patient already had a pregnancy test during their hospitalization, the results will be extracted from the EMR and used to determine eligibility.
6. The designated research team member will randomize the subject. The randomization will be computer generated using this website in a block of 10. (<https://www.sealedenvelope.com/simple-randomiser/v1/lists>).
7. If the subject is randomized to the “study arm”, then the Research Pharmacy will enter in the order for the IVIG and will not charge the subject. If the subject is randomized to the SOC arm, there is no additional work to be completed by the Research Pharmacy.
8. There are 3 endpoints for this study: discharge to home, receipt of mechanical ventilation, or death. Once one of these endpoints is reached, the subject’s participation in the study will end. As such, the subject may be a candidate for enrollment in another research protocol where appropriate.

Dose: IVIG (Octagam) 0.5g/kg IVPB actual body weight daily x 3 days, with premedication methylprednisolone 40 mg IV push x 1 30-50 minutes before each IVIG infusion.

- Initial infusion rate of IVIG (Octagam) will be of **0.6 mL/kg/hour**, increasing to a maximum rate of 100ml/hr, if tolerated. This is consistent with the standard of care for IVIG at Sharp HealthCare.

Procedure Classification: Aside from a urine or blood pregnancy test for subjects of childbearing potential, there are no other extra tests, imaging scans or procedures that will be performed as part of the study.

Potential Hazards and Precautions: Potential hazards to subjects are described in the “Potential Risks” section, and precautions for subjects are described in the “Protection Against Risks” section.

Research team members will take precautions to minimize exposure to COVID-19 infection by obtaining informed consent electronically, and by collecting data from routine clinical tests as opposed to conducting protocol-specific tests.

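### The trial compares IVIG with methylprednisolone premedication plus SOC against SOC, but the title, objectives, hypothesis and design statement attribute the effect to IVIG alone

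*Combined protocol and SAP*

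**What the plan says.** The Dose section specifies Octagam 0.5 g/kg daily for three days, "with premedication methylprednisolone 40 mg IV push x 1 30-50 minutes before each IVIG infusion". Protection Against Risks gives the reason for the premedication: to prevent infusion reactions. For the control arm no drug is specified; Procedures and Study Visits says "If the subject is randomized to the SOC arm, there is no additional work to be completed by the Research Pharmacy".

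The statements of what the trial will show do not mention the steroid:

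- Title: SOC plus IVIG compared with SOC alone.
- Primary Objective: "To identify whether or not IVIG can halt the progression to respiratory failure requiring mechanical ventilation".
- Secondary Objectives: the first reads "To identify whether adding IVIG to the standard of care will reduce days requiring oxygen therapy"; the second has the same form, with length of hospital stay as the outcome.
- Hypothesis: "We hypothesize that the addition of IVIG will be beneficial in abating acute lung injury".
- Study Design: "to compare the impact of adding IVIG to the Standard of Care (SOC) to the SOC without IVIG".

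On data, the case report form paragraph names concomitant antimicrobials and refers in general terms to standard-of-care interventions. Data Analysis plans a description of medications received, without naming a class. The source is the electronic medical record.

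**The concern.** A conclusion written in the words of the primary objective would be about IVIG by itself. What the randomised comparison estimates is the effect of a regimen: IVIG together with an intravenous corticosteroid given before every infusion. If the arms differ, the data cannot say how much of the difference belongs to either drug. A benefit could be credited wholly to IVIG when the steroid contributed to it. A null or adverse result could equally be read as a verdict on IVIG alone.

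A smaller, separate matter is steroids ordered by clinicians outside the regimen. The trial is open label and the visible text does not restrict steroids in SOC, so such use could differ by arm. A reader could judge this only if the use is collected and shown.

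**Working it through.** The plan states no figure for a steroid effect, so there is none to reproduce. The check sets the regimen beside the claims.

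**1. What differs between the arms by protocol**

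| | IVIG arm | SOC arm |
|---|---|---|
| SOC | yes | yes |
| IVIG (Dose section) | 0.5 g/kg daily x 3 | none |
| Methylprednisolone (Dose section) | 40 mg before each infusion | none specified |

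Maximum protocol steroid per IVIG-arm patient = infusions x dose = 3 x 40 mg = 120 mg. It is a maximum because Termination of the Study withholds remaining doses on transfer to intensive care, stops IVIG on mechanical ventilation and lets the patient stop study drug. Protection Against Risks also lets the clinician stop IVIG for side effects.

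**2. What the plan says it will conclude**

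Statements worded as the effect of IVIG: title 1 + primary objective 1 + secondary objectives 2 + hypothesis 1 + design statement 1 = 6. None of the six names methylprednisolone.

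**3. Can the contrast support those statements?**

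Write the expected difference between arms as the effect of (IVIG + premedication + SOC) minus the effect of SOC. No arm receives IVIG without the steroid, and no arm is assigned the steroid without IVIG. One contrast cannot identify two component effects. This is a matter of identification, so more patients would not help. The contrast for the whole regimen is protected by randomisation and is identified.

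**4. How large could the misattribution be?**

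The documents do not say. The Background bases the trial on immunomodulation in severe disease but does not mention steroids; that a steroid might contribute is my inference. As an illustration only, assume that IVIG has no effect, that the SOC risk of ventilation is p, and that the steroid has risk ratio RR. The difference credited to IVIG is then p x (1 − RR):

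| Assumed p | Assumed RR | p x (1 − RR) |
|---|---|---|
| any of 0.20 to 0.60 | 1.0 | 0 points |
| 0.40 | 0.80 | 0.40 x 0.20 = 8 points |
| 0.50 | 0.65 | 0.50 x 0.35 = 17.5 points |
| 0.60 | 0.50 | 0.60 x 0.50 = 30 points |

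Over p from 0.20 to 0.60 and RR from 1.0 to 0.5, the range is 0 to 30 percentage points. Every input is assumed. The table shows that the answer depends wholly on an unknown; it does not estimate a bias.

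**5. Steroids outside the regimen**

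No eligibility criterion or treatment rule in the visible text limits steroids. The exclusion "Active participant in another research treatment study" concerns other trials and does not reach steroids that a clinician orders as routine care. The named case report form drugs are antimicrobials, a list in which a steroid would not be expected, so its absence there shows little. The general references to standard-of-care interventions and medications may cover steroids, but they do not assure that drug, dose and dates will be available in both arms.

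**The case against.** The strongest reply is that this is wording and not a design flaw. The premedication is openly stated, its purpose is to make the infusion tolerable, and naming a regimen after its investigational drug is ordinary shorthand. Anyone who reads the Dose section knows what was given. Nothing in the documents shows that up to 120 mg of methylprednisolone affects ventilation, oxygen days or length of stay. Steroids ordered as SOC are part of the comparator, and the planned description of medications may already pick them up.

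Much of this stands. The premedication is disclosed, the comparison is valid for the regimen, no bias has been shown, and the data-collection point is partly covered. Two things remain. First, the purpose of a drug does not limit its effects. The protocol itself treats methylprednisolone as a distinct exposure: its reasoning for excluding pregnant women cites the lack of adequate studies of methylprednisolone as well as the unknown fetal risk of Octagam. Second, the objectives and the conclusion are what will be cited, and as worded they claim more than the contrast can show.

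A reader might go further and infer that the trial is confounded and its comparison unusable. The documents do not support that: the arms are randomised and the package contrast is sound. Nor do they support saying that steroid use will go unrecorded, or that SOC patients will receive no steroids. The text is general on the first and silent on the second.

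**Conclusion.** The point holds as one of attribution. The trial can estimate the effect of IVIG with methylprednisolone premedication (at most 120 mg by protocol) added to SOC; it cannot estimate the effect of IVIG alone, which is what six statements claim. It should be corrected because, followed as written, the plan leads to a conclusion that the design does not support, and the correction is nearly free.

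The size of any steroid contribution is unknown and could be zero. A reader might infer that any observed benefit would be due to the steroid; the documents give no basis for that either.

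The conclusion rests on the regimen being given as written and on SOC carrying no protocol steroid. Part of the document between the IVIG background and the inclusion criteria was not available to me. It may hold further rationale for the regimen, but rationale would not alter the regimen or the wording of the six statements.

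**What to change.** 1. Restate the title, primary objective, both secondary objectives, hypothesis and design statement, and report the conclusion, as the effect of IVIG with methylprednisolone premedication added to SOC versus SOC alone. This is the step that resolves attribution.
2. As a secondary step, name systemic corticosteroids (drug, dose, start and stop dates) among the medications to be extracted from the electronic record in both arms. Tabulate baseline use and non-protocol use after randomisation by arm, descriptively. This shows whether other steroid use was balanced; it does not separate the two drugs within the IVIG arm.

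Treatment, sample size and the planned tests are unchanged. The cost is the rewording of six statements, one more drug class to extract for 40 patients, and a less specific conclusion about IVIG.

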Study Timeframe: The study time frame would be from IRB approval date to the end of the pandemic or until our sites reach 40 subjects, whatever comes first. We anticipate that at the current COVID-19 rate, it should take about 6 weeks to enroll all patients from the time of study initiation.

The end of study for each individual subject will be the date of discharge from the Sharp HealthCare hospital. The subject will not be followed if there is a transfer to a non-Sharp hospital or any sub-acute care setting (i.e., SNF, LTAC, rehabilitation center). A subject's participation will also end if the subject's goals of care have transitioned to palliation, including changing the code status to Do Not Resuscitate or Do Not Intubate of which would render the patient no longer a candidate for intubation.

Method of Subject Identification and Recruitment: The PI or Sub-I will be notified of a COVID-19 confirmed positive patient via hospital generated alert as part of the Infectious Disease Team at each hospital.

Subject Capacity: Subjects who are cognitively impaired or lack the capacity to provide informed consent (as described in HRP-013 section 5.2) may be enrolled in the study if they have an appropriate LAR to provide written informed consent on their behalf. The researchers will follow the guidance outlined in HRP-013 "Legally Authorized Representatives (Surrogate Consent)" when obtaining surrogate consent.

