Data Collection/ Assessment Instruments: The Case Report Form will include the following data elements: Demographics (age, gender, race/ethnicity, insurance), medical status (pre-existing comorbid conditions (based on the Charlson Comorbidity Index), ferritin level (results will only be collected if lab is ordered as part of the subject's standard of care), CRP level. The tool used to calculate the Charlson Comorbidity Index can be found here <https://www.mdcalc.com/charlson-comorbidity-index-cci#next-steps>). Other data to be collected from standard of care procedures includes vital signs, result of blood or urine pregnancy test, serum creatinine, calculated creatinine clearance (Cockcroft and Gault equation), white blood cell count, platelet count, maximum body temperature in the past 24 hours and oxygen demand rate, whether or not there is an admission to the ICU, any concomitant antimicrobials including azithromycin, doxycycline, hydroxychloroquine, chloroquine, and remdesivir. Receipt of interventions will include standard of care in those who have tested positive for COVID-19. Measures of healthcare service utilization will include length of stay, number of days in ICU, number of days requiring oxygenation, discharge disposition and mortality.

Data Collection Resources: The Study Coordinator will complete the Case Report Forms, with assistance from Sharp's Clinical Analytics team to extract information from the EMR.

Data Analysis: Descriptive statistics will be conducted to describe frequencies of demographics and clinical characteristics including the following: age at discharge, gender, race/ethnicity, payer, comorbid conditions based on the Charlson Comorbidity Index, receipt of medical interventions (mechanical ventilation, medications) and healthcare service utilization (ICU admission and Length of Stay in the hospital). Frequencies and descriptive statistics will be conducted using chi-square or 2-tailed Fisher exact statistics depending on the final sample size for categorical data and t-tests for continuous data. Kaplan-Meier analysis will be performed with assistance from a biostatistician regarding the endpoints of mechanical ventilation and discharge to home endpoints. We do not anticipate number of patient deaths for be sufficient for a meaningful analysis.

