Privacy of Subjects: There will be limited access to the subject due to standard of care isolation protocols. The Informed Consent process will emphasize the personal nature and privacy

concerns related to communications regarding the subject's condition and infectious disease test results.

Confidentiality of Data and Storage: Subjects information will be recorded on a master list accessible to the investigator and research staff. It will be stored electronically on a secure server. Information included on master list: subject ID, hospital, date screened, patient name/room#, FIN, group, age, gender, enrollment status, telephone number, email address, and address. All binders will be stored and secured at Sharp's Center for Research office in accordance with all regulatory and organizational requirements, and will be accessed only by authorized personnel. No subject-specific data will be reported. Sharp FIN will be used to link subject records across data systems and hospital visits. Protected Health Information (PHI) will be safeguarded as specified by Sharp HealthCare policy. There is a risk of disclosure of PHI from inappropriate access to the study database. All efforts will be made to protect PHI, including password protecting the database with access only allowed to study members who are Sharp HealthCare employees. All datasets will be de-identified prior to any statistical analyses conducted by the Statistician. Identifiers will be destroyed two years after study end date, once data has been aggregated for reporting.

Data Monitoring: A designated person (or group of designees) who is not part of the Research Team will review and will report the outcomes to the SHC IRB after a total of 10, 20, and 40 patients (5, 10, and 20 in each arm, respectively) have completed/met the endpoint of the study. Additionally, if unexpected adverse outcomes are identified at any point in the enrollment the designated person will review the case on an individual basis.

Benefits to Individual Subjects: Potential reduction in ICU hospitalization, potential avoidance of mechanical ventilation and potential decrease in length of stay in the hospital.

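### Follow-up stops at transfer, and transfer is none of the three endpoints, so later ventilation or death can go unseen and the discharge-to-home analysis has no outcome for these subjects

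*Combined protocol and SAP*

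**What the plan says.** The primary objective, on the first page of the protocol, is "To identify whether or not IVIG can halt the progression to respiratory failure requiring mechanical ventilation". No time window is attached to it.

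Procedures and Study Visits, item 8, states: "There are 3 endpoints for this study: discharge to home, receipt of mechanical ventilation, or death". Participation ends when one of these is reached.

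Study Timeframe sets the end of observation: "The end of study for each individual subject will be the date of discharge from the Sharp HealthCare hospital". It then adds: "The subject will not be followed if there is a transfer to a non-Sharp hospital or any sub-acute care setting". The sub-acute examples given are SNF, LTAC and rehabilitation. The list under Termination of the Study includes discharge to home but not transfer.

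Data Sources names only the Sharp electronic medical record. Under Data Collection/ Assessment Instruments the case report form includes "discharge disposition and mortality", so a transfer can be identified.

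The Data Analysis section plans two kinds of comparison. One is "chi-square or 2-tailed Fisher exact statistics depending on the final sample size for categorical data and t-tests for continuous data". The other is time to event: "Kaplan-Meier analysis will be performed with assistance from a biostatistician regarding the endpoints of mechanical ventilation and discharge to home endpoints". It states no censoring rule, competing-event method, missing-data rule or sensitivity analysis.

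**The concern.** Where a patient goes on leaving a Sharp hospital depends on how the patient is doing. A patient moved to another acute hospital or an LTAC may be deteriorating, and may be ventilated or die there unseen. A patient moved to SNF or rehabilitation has left acute care alive and unventilated, yet does not meet the favourable endpoint, which is discharge to home only.

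If an analyst censors these subjects at transfer, Kaplan-Meier assumes that their later risk matches that of patients still in the hospital. That is unlikely for either group, and the two groups depart from it in different directions. The trial is open label, so clinicians who know the arm make the transfer decisions, and both the frequency and the type of transfer may differ by arm. With at most 40 subjects, a very small number of unseen events matters.

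Two further items are touched. Oxygen days and hospital days, the secondary objectives, are cut short at transfer. Data Monitoring schedules its reviews by the number of patients who have completed or met the endpoint, and it is unclear whether a transferred patient counts.

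**Working it through.** **No plan figure to reproduce.** The documents give no power, effect size, event rate, transfer rate or dropout allowance. The one relevant piece of arithmetic is consistent: 40 subjects at 1:1 is 40/2 = 20 per arm, as Data Monitoring says. Everything below is illustration on assumed inputs.

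**What is known after each exit, following the text as written**

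| Exit | Ventilation during Sharp stay | Ventilation or death afterwards | Outcome in discharge-to-home analysis |
|---|---|---|---|
| Home | known | not followed | event |
| SNF or rehabilitation | known | not followed | none defined |
| Another acute hospital or LTAC | known | not followed, and plausibly at risk | none defined |

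The last two rows are the gap.

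**Illustration 1: ventilation comparison.** Inputs: 20 per arm (documents); 2/20 IVIG and 9/20 control ventilated, with transfers counted as not ventilated (assumed); two-sided Fisher exact test (named in the plan); 0.05 threshold (assumed, since no alpha is stated). Risk difference = IVIG count/20 − control count/20.

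| Unseen later ventilations | IVIG | Control | Difference (points) | p |
|---|---|---|---|---|
| none | 2/20 | 9/20 | 10 − 45 = −35 | 0.031 |
| 1, IVIG | 3/20 | 9/20 | 15 − 45 = −30 | 0.082 |
| 1, control | 2/20 | 10/20 | 10 − 50 = −40 | 0.014 |
| 1 in each arm | 3/20 | 10/20 | 15 − 50 = −35 | 0.041 |
| 2, IVIG | 4/20 | 9/20 | 20 − 45 = −25 | 0.176 |
| 2, control | 2/20 | 11/20 | 10 − 55 = −45 | 0.006 |
| 4, IVIG | 6/20 | 9/20 | 30 − 45 = −15 | 0.514 |
| 4, control | 2/20 | 13/20 | 10 − 65 = −55 | 0.001 |

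Each unseen event moves the difference by 1/20 = 5 points.

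**Illustration 2: discharge to home.** Inputs, all assumed: constant total exit hazard L = 0.1 per day, horizon T = 28 days, share ventilated v = 0.20, share transferred t, share going home h = 1 − v − t. Deaths are ignored. Ventilation is handled as a competing event in both formulas, so only the treatment of transfer differs.

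- Transfer as a competing event: h × (1 − exp(−L·T)).
- Transfer censored: h/(h+v) × (1 − exp(−L·(h+v)·T)).

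For t = 0.05, h = 0.75. The first is 0.75 × (1 − exp(−2.8)) = 0.704. The second is (0.75/0.95) × (1 − exp(−2.66)) = 0.734.

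| Transferred | Competing event | Censored | Excess |
|---|---|---|---|
| 5% | 0.704 | 0.734 | about 3 points |
| 10% | 0.657 | 0.715 | about 6 points |
| 20% | 0.564 | 0.670 | about 11 points |

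These are errors within one arm. If transfer shares are equal across arms, much of the error may cancel in the comparison; if they differ, it does not.

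**The case against.** The strongest reply is that ventilation is in effect an in-hospital outcome. The data source is the Sharp inpatient record and each subject's study ends at Sharp discharge. On that reading, a SNF or rehabilitation transfer is as fully classified for ventilation as a home discharge, which is not followed afterwards either. This stands, and it narrows the primary-endpoint problem to transfers to another acute hospital or LTAC. It does not remove the problem, because the plan never defines the endpoint that way and an acute-hospital transfer would still leave the risk period partly unobserved. It also does not help the discharge-to-home analysis.

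A second reply is that the plan never says transfers will be censored. That is correct: the Data Analysis section is silent, so the statements about censoring are conditional.

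A third is that the illustrations are extreme. One unseen ventilation in each arm of the 2/20 versus 9/20 example gives p=0.041, hardly a change from 0.031. The larger swings need the unseen events to fall in one arm only. This also stands: the one-arm rows are bounds, not expected values.

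A reader might infer that transferred subjects are deleted from the analysis. The documents do not say so. Follow-up ends, but earlier data and disposition are kept.

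**Conclusion.** The concern holds in a limited form. The plan's own rule stops observation at an event that none of its endpoints covers. For the primary objective, the exposure is ventilation or death after transfer to another acute hospital or LTAC. For the discharge analysis, it is every transfer. If transfers are censored, the censoring depends on clinical state and may differ by arm.

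The size and direction of any bias cannot be derived from the documents, which give no transfer rate. Under the assumed 2/20 versus 9/20, one unseen later ventilation is enough to put p on either side of 0.05 (0.082 or 0.014). Under the assumed hazards, censoring transfers overstates day-28 discharge to home by about 3 to 11 points for 5% to 20% transferred.

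It would go too far to infer that transfers could reverse the trial's result. In every row of the ventilation table the difference still favours IVIG. What changes is the strength of evidence, and that under assumed counts. The issue should be corrected because the rule touches the primary endpoint and the correction is inexpensive.

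**What to change.** 1. In Procedures and Study Visits, item 8, and in Data Analysis, use the recorded disposition to count live, unventilated discharge to home, SNF or rehabilitation as discharge from acute care. Do not count transfer to another acute hospital or LTAC as a success. Counting any destination would score a deteriorating patient as a good outcome.
2. In Study Timeframe, replace the rule that transferred subjects are not followed with ventilation and vital status at one common fixed day, for example day 28, for all randomized subjects. Contacting only transferred subjects would give unequal observation windows. Obtain status by phone or email from the subject or legally authorized representative, with consent text allowing it. The master list already holds "enrollment status, telephone number, email address, and address". Amend the sentences that end participation at an endpoint or at discharge so that this contact remains possible, and add it to Data Sources.
3. In Data Analysis, analyze discharge by cumulative incidence with ventilation and death as competing events. For the ventilation comparison, give best-case and worst-case bounds for anyone whose status is unknown.

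The cost is up to 40 short coordinator contacts and a consent revision. Some subjects will not be reached: inclusion criterion 5 accepts a phone in the hospital room, so a listed number may not work after discharge. Self-reported ventilation is also less exact than the medical record. Steps 1 and 3 need only wording, and are worth making even if step 2 proves impractical.
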